The ApneaLink Air (AL) device is a type III HSAT device. The device is capable of recording up to four channels of data including: flow and snore via a nasal cannula attached to a pressure transducer, a respiratory effort belt, a pulse oximeter to measure pulse and oxygen saturation, and an actigraphy monitor to measure TST along with flow. The AL device has been validated against PSG for AHI^{8,9} and Cheyne-Stoke respiration detection¹⁰. Further validation of the effort belt is necessary to determine the accuracy of the AL ability to differentiate between obstructive and central apneic events.

In 2012, the American Academy of Sleep Medicine (AASM) changed the criteria needed to score a hypopnea during a sleep study. Previous 2007 criteria had required a hypopnea to include a decrease in oronasal airflow by $\geq 30\%$ from baseline for at least 10 seconds and $\geq 4\%$ SpO₂ desaturation¹¹. These criteria have been widely accepted by healthcare providers to form the basis of reimbursement for patient equipment. In 2012, a change was made to these criteria which permitted hypopneas to be scored with an arousal only, or an oxygen desaturation of $\geq 3\%$. This change in rules significantly increases the percentage of patients who may now be diagnosed with OSA, potentially by up to 40%. The need for HSAT devices to detect sleep arousal is now evident with the 2012 AASM update. The AL contains software to detect respiratory effort related arousals (RERA) and score hypopneas using the new 2012 AASM arousal criterion, however, the algorithm has not been validated.

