3.2 Secondary Objectives

The secondary objectives of the study are:

- Compare AL and PSG numbers of obstructive and central events using the effort band and flow sensor per AASM 2012 and 2007 Guidelines
- Evaluate the AL capability to accurately calculate monitoring time per AASM 2012 and 2007 Guidelines
- Evaluate the AL capability to accurately score hypopneas using the AASM 2012 arousal criterion (using monitoring time) vs PSG
- Estimate the positive likelihood ratio in diagnosing SDB of AL compared to PSG and evaluate it per AASM 2012 and 2007 Guidelines against the threshold of 5

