4.9 Endpoints

Primary endpoint:

- Sensitivity in diagnosing SDB of the AL device using AASM 2012 guidelines.

Secondary endpoints:

- The number of predominant obstructive and predominant central events using the AL effort band and flow sensor vs. PSG per AASM 2012 and 2007 Guidelines
- Monitoring times from AL vs total sleep time from PSG per AASM 2012 and 2007 Guidelines
- Number of hypopneas using the AASM 2012 arousal criterion (using monitoring time)
- Positive likelihood ratio in diagnosing SDB using AASM 2012 and 2007 guidelines

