5 STATISTICAL ANALYSIS METHODS

Analysis Populations:

All subjects who meet the inclusion and exclusion criteria and who complete at least 4 evaluable hours will be included in the Intention-to-Treat population (ITT). All primary and secondary analyses will be generated for the ITT population.

Primary Analysis:

The diagnostic sensitivity of AL will be estimated as the number of participants with REI \geq 5 events per hour according to AL per AASM 2012 Guidelines divided by the number of participants with AHI \geq 5 events per hour according to PSG. The diagnostic sensitivity of AL will be compared to the threshold of 0.825 (AASM criteria for out-of-center testing devices) with an exact binomial test, using a significance level of 0.025. Further a one-sided 97.5% confidence interval for the diagnostic sensitivity will be calculated using the Wilson score method.

Secondary Analyses:

To compare the numbers of predominant obstructive and predominant central events measured by AL and PSG, each patient will be classified as having (1) fewer than 5 events per hour, (2) 5 to 10 events per hour, (3) 10 to 30 events per hour or (4) more than 30 events per hour. The categories obtained by AL and PSG will be compared with the weighted kappa statistic. Events will be assessed per both the AASM 2012 and 2007 guidelines.

To compare the AL monitoring times to the PSG total sleep times, Bland-Altman plots will be constructed and the 95% limits of agreement will be calculated. Times will be assessed per both the AASM 2012 and 2007 guidelines.

To compare the number of hypopneas measured by AL and PSG, the number of hypopneas per hour will be categorized as follows: (1) fewer than 5 events per hour, (2) 5 to 10 events per hour, (3) 10 to 30 events per hour or (4) more than 30 events per hour. The categories obtained by AL and PSG will be compared with the weighted kappa statistic. Events will be assessed per both the AASM 2012 and 2007 guidelines.

The positive likelihood ratio (the estimated sensitivity divided by 1 minus the estimated specificity) will also be calculated along with the associated one-sided 97.5% confidence interval. The positive likelihood ratio will be compared with the threshold of 5 (AASM criteria for out-of-center testing devices¹²) using a Wald test. The positive likelihood ratio will be calculated per the AASM 2012 and 2007 guidelines.

AEs

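### The secondary hypopnea endpoint is analysed only by a four-band weighted kappa, which gives no signed bias and only a coarse trace of the size of miscounting; bias and limits of agreement should be added

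*Combined protocol and SAP*

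**What the plan says.** Section 2 explains the interest in this endpoint: AL contains software to "score hypopneas using the new 2012 AASM arousal criterion, however, the algorithm has not been validated". Section 3.2 turns this into a secondary objective: "Evaluate the AL capability to accurately score hypopneas using the AASM 2012 arousal criterion (using monitoring time) vs PSG". Section 4.9 lists the matching endpoint as a number of hypopneas.

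Section 5 gives the whole analysis. "To compare the number of hypopneas measured by AL and PSG, the number of hypopneas per hour will be categorized as follows": fewer than 5, then "2) 5 to 10 events per hour, (3) 10 to 30 events per hour or (4) more than 30 events per hour". Next, "The categories obtained by AL and PSG will be compared with the weighted kappa statistic", and "Events will be assessed per both the AASM 2012 and 2007 guidelines". No weights, cross-table, mean difference or limits of agreement are specified for hypopneas. The preceding paragraph of Section 5, on AL monitoring time against PSG total sleep time, does plan them: "Bland-Altman plots will be constructed and the 95% limits of agreement will be calculated".

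Section 4.7 defines the 2012 hypopnea as a flow reduction with either a desaturation of at least 3% or an arousal. The 2007 hypopnea needs a desaturation of at least 4%. Section 4.7 also gives the two indices different denominators: total sleep time for PSG and monitoring time for AL.

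**The concern.** The objective is accuracy of scoring and the endpoint is a count. A reader of the results will want to know whether AL counts too many or too few hypopneas, and by how much. Banding discards most of that, and kappa condenses the rest into one unsigned number. Three devices with quite different faults can then produce the same result.

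A second limit concerns arousals. The 2012 total pools events that qualify by desaturation with events that qualify by arousal, so agreement on the total bears on arousal scoring only indirectly. Comparing the 2007 and 2012 kappas helps somewhat, but the desaturation threshold moves from 4% to 3% at the same time as the arousal route is added.

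What is at stake is how informative one secondary endpoint will be. No hypothesis test or success threshold is attached to it.

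**Working it through.** **The plan's own figures.** None is given for this endpoint. The only sample-size figure, 56 participants with SDB for the primary test, reproduces: an exact one-sided binomial test against 0.825 rejects at 52 or more of 56, with alpha 0.0229 and power 0.853 at a true sensitivity of 0.95. This point does not touch it.

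**Checks that need no assumptions.**

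- *Size within a band.* 29 and 11.6 both fall in 10 to 30, so they agree fully. 9.9 and 10.1 fall on either side of 10, so they disagree.
- *A constructed case of 75 pairs (PSG, AL):* 15 of (4.9, 0.5), 20 of (9.9, 5.1), 25 of (29, 10.5) and 15 of (70, 31). Every pair stays in its band, so kappa = 1.00. Mean difference = -(15×4.4 + 20×4.8 + 25×18.5 + 15×39)/75 = -1209.5/75 = -16.1/h.
- *Direction.* Weighted kappa = 1 - Σw·O/Σw·E, where O and E are the observed and chance-expected cell proportions and w the disagreement weights. With symmetric w, transposing the table leaves it unchanged. In one simulated sample of 75, linear kappa was 0.596 both ways round, while the mean bias went from -4.1 to +4.1/h.
- *Band edges.* Exactly 10/h belongs to two bands. Exactly 30/h is covered once.

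**Illustration with assumed inputs.** The documents give no rate distribution or error size. Assume the PSG rate P is lognormal with median 12/h and log-SD 0.9, so its mean is 12×exp(0.405) = 17.99/h. Bands are cut at 5, 10 and 30, with linear weights. Limits are bias ± 1.96 SD of the differences, and the half-width of the 95% CI for the bias is 1.96 SD/√75.

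| AL behaviour | Linear kappa | Bias (/h) | 95% limits (/h) | CI half-width, n=75 |
|---|---|---|---|---|
| 20% under-count, 10% noise | 0.79 | -3.5 | -12.3 to 5.3 | 1.0 |
| 25% over-count, 10% noise | 0.79 | +4.6 | -7.4 to 16.6 | 1.4 |
| Unbiased, 28% noise | 0.79 | 0.0 | about ±15 | 1.7 |

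The biases can be checked by hand. Lognormal noise of 0.1 multiplies the mean by exp(0.005) = 1.005, so 17.99×(0.8×1.005 - 1) = -3.5 and 17.99×(1.25×1.005 - 1) = +4.6. Over medians of 8, 12 and 20/h and log-SDs of 0.7, 0.9 and 1.1, the shared kappa ranges from 0.72 to 0.83, the matching over-count is 25 to 26% and the matching noise 28%.

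**Arousal scoring.** Keep the same distribution for hypopneas with at least 3% desaturation. Add arousal-only events proportional to it, at 25% of the total, and assume 70% of the desaturation events reach 4%. Mean total = 17.99/0.75 = 23.99/h, of which 6.00/h is arousal-only. Noise is 10%.

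- *AL detects no arousal-only event:* kappas 0.93 (2007) and 0.74 (2012). Bias = 17.99×1.005 - 23.99 = -5.9/h.
- *AL detects every arousal-only event but misses all events of 3% to under 4%:* kappas 0.93 and 0.75. Bias = (0.7×17.99 + 6.00)×1.005 - 23.99 = -5.3/h.

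The CI half-widths of these biases at n=75 are about 2 and 1.6/h, so Bland-Altman on the total rate does not separate the two devices either.

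**Denominators.** If AL and PSG count the same events, the ratio of their rates is total sleep time divided by monitoring time. Monitoring time 25% longer than total sleep time gives 1/1.25 = 0.80, an apparent 20% under-count with perfect counting. A rate comparison alone therefore mixes count error with time error.

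**The case against.** *Other planned analyses carry direction.* This stands in part. Under-counting lowers sensitivity and over-counting lowers specificity, which enters the positive likelihood ratio. Applying the 5/h cut-off to the three illustrative devices gives sensitivity/specificity of 0.92/1.00, 1.00/0.68 and 0.95/0.87. So it would be wrong to infer that the plan is blind to direction. But the planned measures use apneas plus hypopneas at one cut-off, and in this model only about 12 of 75 participants lie below 5/h. They do not quantify hypopnea miscounting.

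*Weighted kappa is not silent on size, and its table shows direction.* Also true. Larger band jumps are penalised more. In the under-count case about 16 of 75 participants change band, essentially all to the same side of the diagonal. But the weights are not stated and the table is not named as an output.

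*Agreement on bands is a recognised choice, and the plan uses it for obstructive and central events too.* Agreed. This is a reason to keep the kappa, but not to make it the only analysis of a count when the same section already uses limits of agreement for times.

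*The plan does not say that this kappa will validate arousal scoring.* Correct. A reader might infer such a claim from the Background and the objective together, but Section 3.2 says only that the capability will be evaluated. The point concerns what the result can support.

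**Conclusion.** The concern holds as an improvement to one secondary analysis. As written, the hypopnea result will give no signed bias and only a coarse ordinal indication of size. Under the assumed distribution, a kappa of about 0.79 fits a 20% under-count, a 25% over-count or unbiased 28% noise, which differ by about 8/h in mean bias from one extreme to the other (-3.5 to +4.6). The symmetry of kappa and the within-band examples need no assumptions; the other figures are illustrations whose inputs the documents do not supply.

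Two stronger readings are not supported. One is that the endpoint goes unanalysed: taken as the total 2012 count, it is analysed, only coarsely. The other is that Bland-Altman on the total rate would settle arousal scoring: in the worked case it gives -5.9 against -5.3/h for two devices with different faults. The primary sensitivity analysis and its sample size are unaffected.

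**What to change.** In Section 5:

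1. Add Bland-Altman bias with 95% CI and 95% limits of agreement for AL against PSG hypopneas, under the 2012 and the 2007 rules, both per hour and as raw counts over the concurrent recording. The raw counts separate count error from the difference between monitoring time and total sleep time. Use ratio-scale or regression-based limits if the spread grows with the mean. Keep the banded kappa, state its weights, show the 4×4 table and assign exactly 10/h to one band.
2. If AL output and central PSG scoring already label the route by which each hypopnea qualified, also report the arousal-only rate (no desaturation of at least 3%) with bias and limits. Sections 4.11.1 and 4.12 list the files and reports but do not say whether such labels exist, so the sponsor would need to check. Otherwise, word the conclusion as agreement on total 2012 hypopneas, not on the arousal component.

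The cost is SAP wording and a little programming on data already collected, plus one check with the sponsor and the central scorer. No participants or procedures are added. Without route labels, the stated conclusion is narrower.

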Comparison of the ApneaLink Air Home Sleep Testing Device to Polysomnography

Investigational Plan

Protocol Number	SLP-17-10-01
Protocol Version and Date	Version 1.0 31 January 2018
Sponsor	ResMed Corp [name]
Sponsor Contact	[name] Medical Affairs [contact]

ClinicalTrials.gov ID: NCT03470493

This protocol has been written in accordance with current applicable guidelines (IDE for USA) as well as all other relevant additional references, medical and legal.

The information herein is confidential and the property of ResMed Corp. It is to be used in confidence for the conduct of the clinical trial according to written agreement.

PROTOCOL REVISION HISTORY

Version No. And Date	Section	Change	Rationale
Version 1.0 31Jan18	n/a	n/a	Original Release

Protocol Synopsis

Study Title	Comparison of the ApneaLink Air Home Sleep Testing Device to Polysomnography
PSG Central Scoring	University of Florida Health Sleep Disorders Center
Study Objectives	
Primary:
 
 Demonstrate the sensitivity in diagnosing Sleep Disordered Breathing (SDB) of the ResMed ApneaLink Air device (AL) compared to PSG is at least 0.825 when results are scored using the AASM 2012 Guidelines. 
Secondary:
 
 Compare AL and PSG numbers of predominant obstructive and predominant central events using the effort band and flow sensor per AASM 2012 and 2007 Guidelines Evaluate the AL capability to accurately calculate monitoring time per AASM 2012 and 2007 Guidelines Evaluate the AL capability to accurately score hypopneas using the AASM 2012 arousal criterion (using monitoring time) vs PSG scoring of hypopneas Estimate the positive likelihood ratio in diagnosing SDB of AL compared to PSG and evaluate it against a threshold of 5 per AASM 2012 and 2007 Guidelines
Study Design	This is a prospective, unblinded, open-label, single group study. All subjects will undergo concurrent ApneaLink Air testing and in-lab polysomnography.

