4.5 Number of Study Sites and Participants

Up to 75 participants meeting the inclusion and exclusion criteria will take part in this study.

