4.8 Sample Size Justification

The sample size for this clinical study will be up to 75 eligible participants undergoing PSG.

Recruitment goals are as follows:

- At least 30 men and at least 30 women
- At least 5 participants in each of the following SDB categories (per PSG):
 - No SDB (AHI <5)
 - Mild SDB (AHI 5-14)
 - Moderate SDB (AHI 15-29)
 - Severe SDB (AHI ≥ 30)
- At least 5 participants with CSA
- At least 5 participants in each of the following BMI categories (applies to both men and women):
 - Normal BMI: < 25.0
 - Overweight BMI: 25.0 – 29.9
 - Obese: ≥ 30
- At least 5 participants in each of the following race categories:
 - White
 - Black
 - Asian

The primary objective of this study is to demonstrate the sensitivity in diagnosing SDB per the AASM 2012 guidelines. Sensitivity will be assessed according to the AASM criteria for out-of-center testing devices. The hypotheses tested are:

$$H_0: \pi \leq 0.825 \text{ versus } H_A: \pi > 0.825$$

where π is the sensitivity of AL in diagnosing SDB (using a cut-off of 5 events per hour as the threshold for SDB and AHI from PSG and REI from HSAT). The hypothesis will be tested with an exact binomial test using a one-sided significance level of 0.025.

The required sample size to achieve 80% power was estimated using PASS 14, Tests for One Proportion Procedure, assuming a true sensitivity of 0.95 (13 out of 13 true positives were correctly classified in a previous study). To achieve an 80% probability of rejecting the null hypothesis, a minimum of 56 SDB participants are required. Seventy-five participants will be enrolled in order to meet recruitment goals.

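### If 56 of at most 75 participants have SDB, a log- or raw-scale Wald test under 2012 rules can never show LR+ above 5, and the plan has no rule for zero false positives

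*Combined protocol and SAP*

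**What the plan says.** The Synopsis makes LR+ a secondary objective, to "evaluate it against a threshold of 5 per AASM 2012 and 2007 Guidelines", and Section 3.2 repeats it. Section 5 defines LR+ as estimated sensitivity over one minus estimated specificity. It says that LR+ "will also be calculated along with the associated one-sided 97.5% confidence interval". It then states "The positive likelihood ratio will be compared with the threshold of 5", a value taken from the AASM criteria for out-of-center devices, and continues "using a Wald test. The positive likelihood ratio will be calculated per the AASM 2012 and 2007 guidelines".

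Section 5 does not give the scale of the Wald test, its variance formula, its level or direction, or what happens when there are no false positives.

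Section 4.8 sizes the study on sensitivity alone: "a minimum of 56 SDB participants are required. Seventy-five participants will be enrolled in order to meet recruitment goals". Section 4.5 makes 75 a ceiling. The only floor for participants without SDB comes from the recruitment goals: "At least 5 participants in each of the following SDB categories (per PSG"), where one category is AHI below 5. No power is stated for LR+.

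**The concern.** The variance of LR+ is driven by the number of false positives among participants without SDB, and a study sized for sensitivity has few such participants. An accurate device has perhaps one false positive or none. With one, the Wald standard error is very large. With none, LR+ is infinite and the Wald variance does not exist.

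LR+ is the only planned diagnosis-level analysis that counts false positives. If the test cannot reach significance at near-perfect accuracy, an accurate device will be reported as not shown to exceed 5, or the result as undefined. The alternative is that the analyst picks a scale or a zero-cell correction after seeing the data, and that choice decides the outcome.

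**Working it through.** **Inputs.** From Section 4.8: 56 SDB participants, at most 75 in total, null sensitivity 0.825, assumed sensitivity 0.95, one-sided level 0.025 for the primary test. From Section 5: LR+ threshold 5 and a one-sided 97.5% interval. Assumed: the LR+ test is one-sided at 0.025 (critical z 1.96), inferred from that interval. Specificity is not given, so 0.90, 0.95 and 0.98 are used.

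**The plan's own figure.** With n = 56 the exact binomial test rejects at 52 or more correct, with true level 0.0229 and power 85.3% at 0.95. Power is at most 78.2% for any n of 55 or fewer. The figure of 56 reproduces.

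**Formulas.** Let TP of n1 SDB participants and FP of n0 non-SDB participants test positive, and LR = (TP/n1)/(FP/n0).
- SE of ln LR: s = √(1/TP − 1/n1 + 1/FP − 1/n0)
- Log z = ln(LR/5)/s
- Raw z = (LR − 5)/(LR × s)

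**Best table with at least one false positive.** Enumerating every table with n1 ≥ 56 and n1 + n0 ≤ 75, both maxima fall at TP 56/56 and FP 1/19:
- LR = 19; s = √(1 − 1/19) = 0.973
- Log z = ln(3.8)/0.973 = 1.37; lower limit 19 × exp(−1.96 × 0.973) = 2.82
- Raw z = 14/(19 × 0.973) = 0.76; lower limit 19 − 1.96 × 18.5 = −17.2, impossible for a ratio

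**No false positives.** 1/FP is undefined. Adding 0.5 to every cell at 56/56 and 0/19 gives LR = (56.5/57)/(0.5/20) = 39.6, log z = 1.48 (lower limit 2.57) and raw z = 0.63. Over all corrected tables the raw maximum is 0.79. At specificity 0.90, 0.95 and 0.98, the probability of 0/19 is 0.90^19 = 13.5%, 0.95^19 = 37.7% and 0.98^19 = 68.1%.

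**How many non-SDB participants the log test needs.** With all SDB participants correct and one false positive, log z = ln(n0/5)/√(1 − 1/n0). This is 1.946 at n0 = 34 and 1.974 at n0 = 35. So at least 35 non-SDB are needed, hence at most 40 SDB of 75, where primary power at 0.95 is at most 69.1%. With the 0.5 correction and no false positives, 39 non-SDB are needed. The uncorrected raw test never exceeds 1.53 at any split of up to 75. At the recruitment floor of 5 non-SDB, one false positive already caps LR+ at 1/(1/5) = 5.

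**Another Wald form.** For Se − 5(1 − Sp), the table 56/56 and 1/19 gives (1 − 5/19)/√(25 × (1/19)(18/19)/19) = 2.88, which rejects. At 56 + 19, Se 0.95 and Sp 0.81 (so LR+ = 0.95/0.19 = 5), its type I error is 8.1% if tables with no false positives count as undefined and 10.0% if all are counted.

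**Koopman score test (constrained estimates at ratio 5).**
- 56/56 and 0/19: z = 2.18, lower limit 5.95
- 53/56 and 0/19: lower limit 5.62
- 48/56 and 0/19: z = 1.98, the smallest TP count that passes
- 56/56 and 1/19: z = 1.61, lower limit 4.06, fails
- With every participant classified correctly, z = √n0/2: 2.00 at 16 non-SDB and 1.94 at 15, so 15 or fewer cannot pass

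| SDB + non-SDB | Power, Se 0.95, Sp 0.95 | Maximum type I error, LR+ = 5, Se 0.80 to 1.00 |
|---|---|---|
| 56 + 19 | 37.7% | 2.1% |
| 57 + 18 | 39% | 2.2% |
| 58 + 17 | 35% | 2.5% |
| 59 + 16 | 9% | 2.8% |
| 60 + 15 | 0% | 0% |

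At 56 + 19, power is 13.5% at Sp 0.90 and 68.0% at Sp 0.98.

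**The case against.** The strongest reply is that the plan never chose the log or raw scale. A reader might infer that the LR+ test as written must fail. The documents do not support that, because a Wald test on Se − 5(1 − Sp) also fits the wording and can reject. Counting tables with no false positives, its power at 56 + 19 and Se 0.95 is about 42%, 75% and 95% at Sp 0.90, 0.95 and 0.98. This part stands, and the claim is limited to the two ratio scales. It does not rescue the plan: those powers come with a type I error of about three to four times 2.5%.

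The 56 is a power requirement and not a quota, and the test level is inferred. Both are true. But the log test becomes workable only with 40 or fewer SDB participants, where the primary test falls short of its 80%. At one-sided 0.05 the ratio-scale tests still cannot reject (1.48 against 1.645), though at 0.10 the log test could.

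It may also be said that an unpowered secondary comparison is to be expected, and that a score test recovers little. Low power is indeed expected, and the number of non-SDB participants stays the main constraint. But a zero chance of success whatever the accuracy of the device is a different matter from low power.

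**Conclusion.** The point holds in this form. Under 2012 scoring, with at least 56 SDB participants within 75 and a one-sided 0.025 test, a log- or raw-scale Wald test cannot show LR+ > 5 for any possible result, with or without a 0.5 correction. Without a correction it is undefined when there are no false positives. The linear Wald form can reject but is anticonservative.

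Three wider inferences are not supported:
- That the analysis is uninformative. The LR+ estimate and its interval still inform when there is at least one false positive, and a ratio clearly below 5 can be detected (53/56 and 10/19 gives log z = −4.65).
- That the primary endpoint is affected. It is not, and the error on the ratio scales is toward not claiming success.
- That the 2007 analysis has the same defect. The SDB split under those rules is not given. The stricter 2007 hypopnea definition in Section 4.7 can only move participants toward non-SDB, where the log test may become workable.

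This is worth correcting before analysis, as a matter for a secondary endpoint.

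**What to change.** In Section 5, replace the Wald test and its interval with one named method: the Koopman score test of LR+ = 5 at one-sided 0.025, with its one-sided 97.5% lower limit. The lower limit is finite when there are no false positives, although the point estimate is then infinite. Use the method for both rule sets for consistency. Name only one method: Miettinen–Nurminen agrees at 56 + 19, but at 58 + 17 and Sp 0.95 its power is 28% against 35%. Stating a ratio scale and a 0.5 rule for the Wald test would not be enough, since z stays at or below 1.48. Report sensitivity and specificity with exact intervals alongside.

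In Section 4.8, state that:
- the LR+ comparison is not powered, with the figures above; at 56 + 19 it passes only with 0/19 false positives and at least 48/56 true positives;
- with 15 or fewer non-SDB participants it cannot pass, and LR+ is then estimation only;
- maximum type I error is about 2.1% at 56 + 19, 2.5% at 58 + 17 and 2.8% at 59 + 16.

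The cost is a change of wording and a standard routine, with no extra participants. The drawbacks are that the plan discloses limited power, which the score test does not remove, and that type I error is slightly above nominal at some splits.
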